2.0 OBJECTIVES AND SCIENTIFIC AIMS

The primary objective for this study is:

 To evaluate whether romiplostim can improve the recovery of persistent, isolated Chemotherapy-Induced Thrombocytopenia (CIT), to a platelet count ≥100,000/mcL within 3 weeks after initiation of therapy.

Secondary Objectives

The secondary objectives for this study are:

- 1. In patients whose platelet counts have recovered within three weeks on romiplostim treatment, we will observe for:
 - a. Ability to resume at least two cycles (or eight weeks, whichever comes first) of chemotherapy without recurrence of chemotherapy-induced thrombocytopenia leading to chemotherapy dose delay or reduction.
 - i. Note the duration of off-chemotherapy time.
 - b. Change in chemotherapy for progression of disease or other cancer related conditions.
 - c. Change in chemotherapy for other toxicities unrelated to thrombocytopenia.
 - d. Censor patients who have tolerated chemotherapy with romiplostim support for up to 12 months.
 - e. Death due to all causes.
- 2. The safety profile of romiplostim will be assessed in this patient population at specified time-points during the course of study as per section 11.0 Toxicities/Side Effects.

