3.4 Rationale for Romiplostim in CIT

At MSKCC, [name], [name], and [name] have treated over 50 patients with romiplostim for CIT. Our initial case series of 20 patients was published in 2014, indicating 19 of 20 treated patients meeting the goal of normalization of platelet count to >100,000/mcL ([name] et al, 2014).

Our interim observations of this current clinical trial suggests that romiplostim is effective and safe to improve platelet counts in patients with CIT. Of the treatment patients, 13 of the 14 (93%) romiplostim patients normalized their platelet count within the three-week primary endpoint. From our initial 21 patients who enrolled on this trial, 1 out of 7 (14.3%) observation patients have corrected her platelet counts within 3 weeks. (P= 0.0009 by two-tailed Fisher's Exact Test). Of the 5 observation patients who crossed over to romiplostim and were evaluable, all 5 corrected their platelet count within 3 weeks. Of all patients receiving romiplostim, 18 of 19 patients (95%) reach platelet counts of 100,000/mcL or greater within 3 weeks of treatment. No patients who resumed chemotherapy while receiving romiplostim (N=14) had a recurrence of CIT. We continue to see efficacy and safety within our patients currently on romiplostim. Based on highly significant efficacy and no further spontaneous correction of platelets, it was felt inappropriate to continue randomizing to the observation control arm.

No toxicity attributable to the romiplostim has been observed in our initial cases. Three of the initial 20 courses of treatment (19 patients) developed deep vein thrombosis which is within the historical range of between 10% and 30% ⁷ in comparable patients with metastatic cancer on chemotherapy. Further, one of the two patients with DVT had a previous history of DVT, prior to initiation of romiplostim, and had been off anticoagulation when the second thrombosis occurred.

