4.0 OVERVIEW OF STUDY DESIGN/INTERVENTION

4.1 Design

Primary objective:

This is an intent-to-treat multicenter phase II open label trial. Once appropriate patients are identified and enrolled, 60 patients will be enrolled.

During the initial 3-week period, the enrolled patients will receive romiplostim, titrated as per protocol (Section 9.0). Assessment for the primary endpoint will take place at week 3 and denote the proportion of patients that achieves a platelet count of >100,000/mcL within 3 weeks of initiation.

Safety Analysis will be performed at specified time-points (Section 11.0 Toxicities/Side Effects) including possible adverse events such as thrombosis, peripheral blood abnormalities and evidence of organ dysfunction.

Secondary objective:

In patients whose platelet counts have recovered within three weeks, we will observe for patient's ability to receive two cycles (or eight weeks, whichever comes first) of cytotoxic chemotherapy without recurrence of chemotherapy-induced thrombocytopenia leading to chemotherapy dose delay or reduction; change in chemotherapy for progression of disease or other cancer related conditions; change in chemotherapy for other toxicities unrelated to thrombocytopenia; and death due to all causes. The duration for patients off-chemotherapy will also be noted. In addition we are also censoring patients who have tolerated chemotherapy with romiplostim support for up to 12 months.

Safety endpoints will include possible adverse events such as thrombosis, evidence of marrow toxicity, and evidence of organ dysfunction.

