The study will report only those toxicities that are not known to be linked to the patient's prior chemotherapy treatment or underlying disease. All toxicities meeting this criteria should be reported to MSKCC as an Adverse Event in CRDBi-Multicenter with supporting source documentation.

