Lastly, the frequency of thrombosis, marrow toxicity, and organ dysfunction will be tabulated.

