17.2.1 Report SAEs to Amgen by MSKCC

The MSKCC research staff must inform Amgen, Inc. of any SAE as soon as possible but no later than 5 calendar days of the MSKCC principal investigator becoming aware of the event. Participating sites should submit SAEs to MSKCC as indicated in section 17.3 and MSKCC will report these events to Amgen as appropriate. Participating sites should not submit SAEs directly to Amgen. All SAE's will be reported up to 30 days after the last dose of treatment.

Definitions

Adverse Event Definition

Adverse event (AE) means any untoward medical occurrence(s) in a patient/subject attributed to a pharmaceutical product. (The untoward medical occurrence does not necessarily have a causal relationship with this treatment.) An AE can therefore be any unfavorable and unintended sign (including an abnormal laboratory finding), symptom, or disease temporally associated with the use of a medicinal (investigational) product whether or not it is related to the medicinal product. This includes any newly occurring event, or a previous condition that has increased in severity or frequency since the administration of study drug.

Serious Adverse Event Definition

Serious adverse event (SAE) means any untoward medical occurrence that at any dose:

- Results in death.
- Is life-threatening (refers to an AE in which the patient was at risk of death at the time of the event. It does not refer to an event which hypothetically might have caused death if it were more severe).
- Requires inpatient hospitalization, with the exception of a planned procedure.
- Requires prolongation of an existing hospitalization.
- Results in persistent or significant disability or incapacity. (Disability is defined as a substantial disruption of a person's ability to conduct normal life functions).
- Is a congenital anomaly/birth defect.
- Is a medically important event. This refers to an AE that may not result in death, be immediately life threatening, or require hospitalization, but may be considered serious when, based on appropriate medical judgment, may jeopardize the patient, require medical or surgical intervention to prevent one of the outcomes listed above, or involves suspected transmission via a medicinal product of an infectious agent.

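### The Section 11.0 attribution filter can remove non-serious thrombosis from a frequency that Section 14.0 presents with no attribution condition

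*Combined protocol and SAP*

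**What the plan says.** **The reporting rule.** Section 11.0 closes with a restriction: "The study will report only those toxicities that are" not "known to be linked to the patient's prior chemotherapy treatment or underlying disease". Toxicities that pass this test are to be sent to the coordinating center as adverse events. For participating sites, Section 16.0.1 asks for source documents only on events that meet the reporting requirements, and the footnote to the chart in Section 16.0.3 ties the Adverse Event Form to Section 11.0. That chart lists no separate thrombosis form. The coordinating center's own data go into its clinical research database under Section 16.0, with no form schedule shown, so for those patients only the general restriction applies.

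**The planned analysis.** Section 4.1 states: "Safety endpoints will include possible adverse events such as thrombosis, evidence of marrow toxicity, and evidence of organ dysfunction". Section 14.0 says that "the frequency of thrombosis, marrow toxicity, and organ dysfunction will be tabulated". Neither attaches a condition on cause, and Section 14.0 does not name the data sources for the table.

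**Other routes into the data.** Sections 17.2 and 17.2.1 require SAEs to be reported up to 30 days after the last treatment, with no such filter. Sections 10.0 and 11.0 schedule laboratory monitoring, and the chart in Section 16.0.3 includes a Laboratory Form that carries no filter.

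**The concern.** The collection rule is narrower than the analysis it feeds. Thrombosis is the named safety event for which the cancer offers the readiest explanation: Sections 3.4 and 11.0 both discuss it against what is expected in metastatic cancer on chemotherapy. An investigator who regards a non-serious clot as known to be linked to the disease would be following Section 11.0 by not reporting it. The protocol does not say who makes that judgement or on what criteria.

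At stake is how the thrombosis frequency can be read. The observation arm was dropped, treatment is open label, and the thrombosis benchmarks in the protocol are external. Section 3.4 quotes a 10% to 30% range for comparable patients, which counts clots without regard to relationship to romiplostim. A rate with disease-linked clots removed would look too low beside it.

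**Working it through.** The documents give no figure to reproduce, so the check traces which events can reach the Section 14.0 table.

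1. **Serious thrombosis.** It is reported as an SAE whatever its cause (17.2, 17.2.1). The SAE definition covers hospitalization, threat to life and medically important events, so many symptomatic clots will qualify. Nothing states that every thrombosis is serious. This route is not filtered.

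2. **Marrow toxicity and most organ dysfunction.** Weekly blood counts and regular chemistry and coagulation tests are recorded on the Laboratory Form regardless of attribution (10.0, 11.0, 16.0.3). This route is largely unfiltered.

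3. **Non-serious thrombosis of uncertain cause.** The filter removes only events with a *known* link, so these should still be reported.

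4. **Non-serious thrombosis linked only to chemotherapy resumed on study.** The restriction names earlier chemotherapy and the underlying disease. Read literally, it does not remove these events.

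5. **Non-serious thrombosis judged known to be linked to the cancer or earlier chemotherapy.** Section 11.0 excludes it from reporting, and the Adverse Event Form and source-document rules follow Section 11.0. No other section gives it a recording route. New anticoagulation might appear on the Concomitant Medications Form, but no section makes that form a source for the thrombosis count.

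Only class 5 is exposed.

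**Direction and size.** Let N be the number of patients in the denominator, T the number with any thrombosis, and m the number of those whose every thrombosis was filtered out. The tabulated frequency is (T − m)/N and the all-cause frequency is T/N. The difference is −m/N with m ≥ 0, so the error is downward or zero.

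Section 14.0 gives 60 evaluable patients and 61 enrolled. Per omitted patient:

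- N = 60: 1/60 = 0.0167, or 1.7 percentage points.
- N = 61: 1/61 = 0.0164, or 1.6 percentage points.

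Estimating m would need the thrombosis rate in this trial, the share that is non-serious, and the share of those judged to have a known link. The documents give neither share, so no total is offered.

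**The case against.** **The exposed class is narrow.** This stands. *Known* is a demanding word, serious events bypass the filter, and Section 11.0 promises to monitor any clinical sign of clotting. Section 9.0 makes continued romiplostim after a symptomatic, non-life-threatening DVT or PE depend on agreement between the oncologist and the study investigator, so the study team would learn of many such events. But monitoring or knowing of an event is not recording it, and the restriction on reporting follows in the same section as the monitoring commitment.

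**Practice may already ignore the filter.** Section 3.4 counts three DVT courses among the first 20 while saying "No toxicity attributable to the romiplostim has been observed in our initial cases". This cuts against any inference that thromboses have been lost. It does not settle the matter, because Section 3.4 does not say whether those DVTs were serious or how they were recorded.

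**Section 11.0 may be meant to govern content.** Section 2.0 has safety assessed "at specified time-points during the course of study as per section 11.0 Toxicities/Side Effects", which cites Section 11.0 for timing. If it also governs which events count, Section 14.0 should say that its frequencies are filtered. Either reading calls for an edit.

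**No planned decision depends on the rate.** Correct: Section 14.0 plans a tabulation, with no safety test and no formal comparison with 10% to 30%. The harm lies in how a reader would interpret the rate.

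**Stronger readings that the documents do not support.** A reader might infer that all three safety categories are undercounted, but laboratory data cover marrow toxicity and most organ toxicity. A reader might set the filter against the adverse event definition in Section 17.2.1, which includes events "temporally associated with the use of a medicinal (investigational) product whether or not it is related to the medicinal product". That definition opens by speaking of occurrences attributed to a product, so it points both ways, and it sits under SAE reporting to the manufacturer. It adds nothing firm.

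**Conclusion.** The point holds in limited form and should be fixed. A stated rule allows non-serious thrombosis judged known to be linked to the cancer or earlier chemotherapy to stay out of a frequency that Sections 4.1 and 14.0 present without any attribution condition.

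The error can only lower the rate. Its total cannot be estimated and may be zero; each omitted patient costs 1.7 percentage points on 60 patients or 1.6 on 61. The conclusion assumes that the Section 14.0 table draws on SAE and laboratory records as well as the Adverse Event Form; if it used the form alone, the exposure would be wider. The documents do not show that any event has been lost. The primary endpoint and the 54-of-60 rule are unaffected.

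**What to change.** 1. **Section 11.0**, and through it 16.0.1 and 16.0.3: exempt thrombosis from the filter. Record every thrombosis regardless of attribution, with relationship to romiplostim, chemotherapy and disease in a separate field. The filter can stay for other toxicities.
2. **Section 14.0**: state that the thrombosis frequency is per patient, all-cause, over all treated patients, from adverse event and SAE data combined, with the attributed subset shown second.
3. **Patients already treated**: establish whether the filter was applied, both in the coordinating center's entries and at the sites. Where it was, recover non-serious thromboses from existing records if that can readily be done. New anticoagulants on the sites' Concomitant Medications Form can serve as a screening flag, though an imperfect one, since Section 6.2 admits patients already on anticoagulation.
4. **Where recovery is not practical**: print the Section 11.0 limit beside the reported rate, and do not read that rate against the 10% to 30% range.

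**Cost.** A minor amendment, which Section 16.3.1 would send to participating-site IRBs unless expedited, and limited record checking among the 61 enrolled patients. Section 14.0 describes enrollment in the past tense, so the wording change may help only patients still on treatment; for the rest, steps 3 and 4 matter most. The thrombosis rate may look less favourable. Printing the limit beside the rate costs almost nothing.

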12.0 CRITERIA FOR THERAPEUTIC RESPONSE/OUTCOME ASSESSMENT

The primary therapeutic response is assessed by the platelet count within 3 weeks of treatment.

1. Achievement of platelet counts of >100,000/mcL in patients who receive romiplostim will serve as the primary endpoint.

The secondary therapeutic response endpoints are:

For patients who successfully achieve platelet counts of \geq 100,000/mcL, and resume chemotherapy, we will observe the:

- Ability to resume two cycles (or eight weeks, whichever comes first) of cytotoxic chemotherapy without recurrence of chemotherapy-induced thrombocytopenia leading to delay or dose reduction in chemotherapy.
 - Dose reduction/ delay for pancytopenia or drop in hemoglobin or neutrophil count will not count.

- b. The day of chemotherapy dose delay/ reduction will be considered the secondary endpoint.
- c. Duration of the off-chemotherapy time will be recorded.
- 2. Change in chemotherapy for progression of disease or other cancer related conditions.
 - a. The start of a new chemotherapy is the day that will be considered the secondary endpoint.
- 3. Change in chemotherapy for other toxicities unrelated to thrombocytopenia.
 - a. The start of a new chemotherapy is the day that will be considered the secondary endpoint.
- 4. Censoring patients who have tolerated chemotherapy with romiplostim support for 12 months.

13.0 CRITERIAFOR REMOVAL FROM STUDY

Treatment will continue until the occurrence of any of the following events:

- Continuation is no longer in the patient's best interest as determined by the patient's oncologist.
- Patient withdraws consent
- Death
- Lost to follow-up
- Major violation of study protocol, such as non-compliance.
- Adverse event(s) that, in the judgment of the Investigator or treating oncologist, may cause severe or permanent harm or which rule out continuation of the trial.
- Discontinuation of chemotherapy for reason other than CIT. If the patient is discontinuing chemotherapy regimen and beginning a different regimen, the patient may remain on study.
- Note: (Patients on romiplostim who fail to achieve ≥100,000/mcL within the first 3 weeks of treatment are considered a primary treatment failure. However, patients can continue on treatment per protocol if the treating physician believes the patient will benefit for secondary endpoints.)

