 - B. The secondary endpoint will be documented for patients whose platelet counts have recovered within three weeks. We will observe for ability to resume 2 cycles (or eight weeks, whichever comes first) of cytotoxic chemotherapy without recurrence of chemotherapy-induced thrombocytopenia leading to chemotherapy dose delay or reduction; change in chemotherapy for progression of disease or other cancer related conditions; change in chemotherapy for other toxicities unrelated to thrombocytopenia; and death due to all causes. The duration for patients off chemotherapy will be noted. In addition we are also censoring patients who have tolerated chemotherapy with romiplostim support for up to 12 months.
 - C. Romiplostim dose titration. After resumption of full-dose chemotherapy, the romiplostim dose can be further titrated based on platelet count at beginning of each chemotherapy cycle. The dose adjustments are from the prior week's romiplostim dose. The below dose titration refers to the initial 2 cycles of resumed chemotherapy as well as the continuation phase for patients who successfully complete the study through 2 cycles.
 - 1. The target platelet count, at initiation of a cycle of chemotherapy is 100,000-200.000/mcL.
 - 2. If the pre-chemotherapy cycle platelet count is >200,000/mcL, the romiplostim dose will be reduced by 0.5 mcg/kg.
 - 3. If the pre-chemotherapy cycle platelet count is >250,000/mcL, the romiplostim dose will be reduced by 1.0 mcg/kg

- 4. If the pre-chemotherapy cycle platelet count is <100,000/mcL, the romiplostim dose will be increased by 1.0 mcg/kg.
- 5. The dose of romiplostim may be rounded off to the nearest 50 mcg.
- 6. The dose of romiplostim may be modified at the discretion of the study investigator in consultation with the MSKCC P.I. Smaller dose increments (or decreases) may be needed to titrate the platelet count to the 100,000-200,000/mcL target.

III. Discontinuation of Romiplostim.

- A. Discontinuation of Cancer Therapy. After the 3 week period of the initial endpoint is reached, if the treating medical oncologist discontinues chemotherapy or switches to a cancer therapy not associated with thrombocytopenia, the romiplostim may be discontinued.
- B. If a patient develops a Grade 3/4 adverse event, attributable to Romiplostim, based on the Common Terminology Criteria for Adverse Events (CTCAE), the Romiplostim will be discontinued.

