14.0 BIOSTATISTICS

This study was originally designed as a phase II randomized study where patients were randomized 2:1 to respectively receive romiplostim and observational control. The primary endpoint was the achievement of a platelet count of ≥ 100,000/mcL within three weeks of study enrollment, and any patient removed from study during evaluation window without count recovery was considered a treatment failure. Based on earlier MSKCC data, it was estimated that the probability of a success in the romiplostim arm is at least 90%, while the probability of a spontaneous recovery in the control arm is 60% or less.

Due to preliminary trial results, the protocol was amended on 4/13/2016 and the observation control arm was dropped. At that point, the study became a single arm phase II study of romiplostim. The sections below represent the new single arm study design.

Analysis of these data will only be done with 60 evaluable patients enrolled on the trial. There was one patient enrolled during this time who was inevaluable and therefore there were 61 patients enrolled for 60 spots.

Primary endpoint:

This study is a single arm phase II design to evaluate romiplostim mediated improvements in platelet counts in patients who have experienced CIT. The primary endpoint is the achievement of a platelet count of ≥ 100,000/mcL within three weeks of study enrollment. Any patient who is removed from study before the evaluation of the primary endpoint will be considered a treatment failure. A total of sixty patients will be enrolled and treated with romiplostim. Based on preliminary MSKCC data, it is estimated that the probability of a success in patients on romiplostim treatment is at least 90%. Therefore, we will consider the trial promising and worthy of further intervention if at least 54 out of 60 achieve platelet count recovery. The operating characteristics of this design rule are provided in the table below.

	True Rate of Count Recovery						
Probability of	0.85	0.875	0.9	0.925	0.95		
Observing >= 54/60	17%	40%	60%	81%	97%		

Secondary endpoints:

Patients who achieve a platelet recovery may be allowed to resume chemotherapy. In these patients, we are observing for recurrence of chemotherapy-induced thrombocytopenia leading to chemotherapy dose delay or reduction; change in chemotherapy for progression of disease or other cancer related conditions; change in chemotherapy for other toxicities unrelated to thrombocytopenia; and death due to all causes.

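### Sections 13 and 9.III.A conflict on patients who stop all chemotherapy for a reason other than CIT, and Section 14 can turn such a stop in weeks 1-3 into a primary-endpoint failure whatever the counts show

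*Combined protocol and SAP*

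**What the plan says.** **Section 13.0 (criteria for removal from study)** opens its list with "Treatment will continue until the occurrence of any of the following events". One listed event is "Discontinuation of chemotherapy for reason other than CIT". No time limit is given, so it applies from the first week. The next sentence makes one exception: "If the patient is discontinuing chemotherapy regimen and beginning a different regimen, the patient may remain on study".

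**Section 9.0, III.A** deals with the same event but begins "After the 3 week period of the initial endpoint is reached, if the treating medical oncologist discontinues chemotherapy". Its consequence is permissive: "the romiplostim may be discontinued". It says nothing about a chemotherapy decision during weeks 1-3.

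**Section 14.0**, for the current single-arm design, states: "Any patient who is removed from study before the evaluation of the primary endpoint will be considered a treatment failure". No reason for removal is exempt. The same section describes the rule of the former randomized design differently: "any patient removed from study during evaluation window without count recovery was considered a treatment failure". The trial is declared promising if "at least 54 out of 60 achieve platelet count recovery".

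**Section 6.1** requires that patients have had no cytotoxic chemotherapy in the 14 days before starting. **Sections 9.0 and 10.0** already specify a weekly CBC for the first 3 weeks.

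**The concern.** Sections 13 and 9.III.A differ in force (treatment ends, or may end) and in timing (any time, or only after week 3). The difference reaches the primary endpoint through Section 14. Take a patient whose oncologist ends chemotherapy in week 2 for progression and starts nothing new. A site following Section 13 ends treatment and may record a removal, which Section 14 scores as a failure. A site guided by the timing in Section 9.III.A may keep the patient on romiplostim to week 3 and score the platelet counts.

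A second problem lies within Section 14. The former rule failed a removed patient only if the count had not recovered. The current sentence has no such condition. Section 4.1 places the assessment at week 3, so a patient who reached 100,000/mcL in week 1 and was removed in week 2 was removed before the evaluation, and fails on the literal wording. Yet the endpoint itself is reaching that count at any point within three weeks, which this patient did.

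The decision rule allows six failures in 60. In a multicenter trial, an oncology decision unrelated to platelets could use one of them at one site and not at another.

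**Working it through.** **Step 1. The passages side by side, for a stop in weeks 1-3 for a reason other than CIT.**

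| Situation | Section 13 | Section 9.III.A | Primary score |
|---|---|---|---|
| Switch to a different regimen | May remain on study | Silent before week 3 | On counts; no conflict |
| Stop, no new regimen, no qualifying count yet | Treatment ends | Silent before week 3; optional later | Failure if treated as removal; on counts if kept on study |
| Stop, no new regimen, 100,000/mcL already reached | Treatment ends | Silent before week 3; optional later | Failure under the current Section 14 sentence; success under the endpoint definition and under the former rule |
| Chemotherapy on hold at entry, decision not to restart | Not stated whether this is a discontinuation | Not stated | Undetermined |

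Two links in the chain are inferred. The heading of Section 13 suggests that end of treatment means removal from study, but the text does not say so. That Section 9.III.A would keep the patient on romiplostim to week 3 follows only from its timing.

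**Step 2. The plan's own operating characteristics.** With X ~ Binomial(60, p), the probability of meeting the rule is P(X ≥ 54).

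| True rate p | 0.85 | 0.875 | 0.90 | 0.925 | 0.95 |
|---|---|---|---|---|---|
| Stated in Section 14 | 17% | 40% | 60% | 81% | 97% |
| Exact binomial | 18.5% | 36.4% | 60.6% | 83.9% | 97.0% |

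The entries at 0.85, 0.90 and 0.95 agree within 2 points; those at 0.875 and 0.925 do not. That is a separate matter and nothing below depends on it. The exact values are used from here.

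**Step 3. Effect of forced failures.** If k of the 60 patients are scored as failures because of removal, all 54 successes must come from the other 60 − k. The probability is P(Y ≥ 54) with Y ~ Binomial(60 − k, p), where p is the recovery rate among those scored on counts.

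| k | p = 0.90 | p = 0.925 | p = 0.95 |
|---|---|---|---|
| 0 | 60.6% | 83.9% | 97.0% |
| 1 | 45.4% | 72.0% | 92.6% |
| 2 | 29.9% | 55.8% | 83.6% |

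One forced failure costs 60.6 − 45.4 = 15.2 points at p = 0.90, the rate the plan assumes as a minimum, and 97.0 − 92.6 = 4.4 points at p = 0.95. The documents give no value for k, so k = 1 and k = 2 are assumptions chosen to show sensitivity.

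**The case against.** - **The reach is narrow.** Section 13 exempts a change of regimen, and the secondary endpoints treat a change of chemotherapy for progression as an expected on-study event. This stands: the conflict concerns only patients who stop and start nothing new.
- **The trigger in weeks 1-3 is partly inferred.** Patients enter with chemotherapy withheld for at least 14 days, and no section equates not restarting with discontinuing. A reader might infer that every decision not to restart triggers Section 13; the text does not establish that. It leaves the question open, which is itself a reason to clarify.
- **The sections can be harmonized.** Section 9.III.A could be read as the specific rule and Section 13 as the general list. That reading is available, but nothing in the documents adopts it.
- **Failure on early removal is a legitimate conservative rule**, and the trial describes itself as intent-to-treat. This stands. A reader might infer that the rule biases the result improperly. It does not do so by itself: if removal is part of the failure definition, the true rate can be taken to include it, and adding k failures on top would count them twice. What remains is that the trigger for removal is ambiguous and that a qualifying count already recorded can be overridden.
- **The problem may be rare.** Section 3.4 reports that 18 of 19 romiplostim patients reached 100,000/mcL within 3 weeks, so at most one of those reported failed for any reason. The crossover patients in that figure were limited to evaluable ones. Section 14 also mentions one inevaluable patient outside the 60, without giving the reason. Neither fact fixes the frequency.
- **Enrollment appears complete**, with 61 patients enrolled for 60 places. New prospective blood counts would then add little, but scoring rules and chart retrieval remain open.

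**Conclusion.** The point holds in a limited form. For patients who stop chemotherapy for a reason other than CIT and start no new regimen, Sections 13 and 9.III.A give different rules and no order of precedence. If a stop in weeks 1-3 counts as removal, Section 14 makes the patient a primary failure regardless of counts. Its present wording also drops the condition that protected a patient who had already recovered.

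The size is unknown. The 15.2-point and 4.4-point losses show how sensitive the 54-of-60 rule is to one reclassified patient. They assume that this patient is removed without credit for any qualifying count and that p applies to the other 59. They do not estimate what happened in the trial, and the documents do not support a claim that the primary result is biased by any particular amount. A patient kept on study could still fail on counts. The matter deserves correction because it can move the primary count and is cheap to settle.

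**What to change.** 1. **Sections 13 and 9.III.A:** reconcile whether, and from when, stopping chemotherapy without a new regimen ends study treatment, and whether deciding not to restart held chemotherapy counts as stopping. Which clinical rule applies is for the investigators.
2. **Section 14, success:** state that a count of at least 100,000/mcL recorded within the 3-week window is a success even if the patient is later removed. Say whether ending treatment in weeks 1-3 is removal for this endpoint.
3. **Section 14, data:** score from the weekly CBCs already specified for weeks 1-3, retrieving them from charts for consenting patients already enrolled. State whether counts taken after romiplostim has stopped, but within the window, are used.
4. **Section 14, default:** keep failure as the score when no qualifying count is available.
5. **Reporting:** show failures separately as no recovery on counts, and as removed with counts not available, with the reason for each removal.

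The cost is a few sentences across these sections, minor chart retrieval for a few patients, and one extra tabulation. The sample size and the 54-of-60 rule do not change.
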